7. PATIENT SELECTION

Investigators will be expected to maintain a screening log of all potential study candidates. Eligibility criteria will be evaluated during screening.

Before any study-specific activity / procedure, the appropriate written informed consent must be obtained.

Prospective approval of protocol deviations to recruitment and enrollment criteria will not be provided.

a. Inclusion criteria

- 1. Age ≥ 18 years of age at the time of signing informed consent.
- 2. Newly diagnosis of primary ITP according to the International Working Group assessment [1] and previously untreated for ITP.
- 3. Platelet counts <30x10⁹/L or ITP with platelet counts <50x10⁹/L and concomitant bleeding symptoms.
- Serum creatinine concentration ≤1.5 mg/dL.

b. Exclusion criteria

- 1. WHO performance status >2.
- Previous therapy with rituximab (within 3 months previous of study enrollment), corticosteroids or therapy with other immunomodulating agents within 1 month before enrolment; prior use of hematopoietic analogs or fostamatinib for any other reason than ITP three months before enrolment.

- 3. Previous use of romiplostim, PEG-recombinant human (rHu) megakaryocyte growth and development factor, eltrombopag, recombinant human anti-thrombopoietin (rHuTPO), or any platelet-producing agent for three months prior to enrolment.
- 4. Alkylating agents within 8 weeks before the screening visit or anticipated use during the time of the proposed study.
- 5. Splenectomy within 3 months of the screening visit or planned splenectomy during study period.
- 6. Abnormal renal function (serum creatinine > 1.5 mg/dL).
- 7. Active hepatic disease evidenced by alanine aminotransferase [ALT] or aspartate aminotransferase [AST] levels >5 times the upper limit of normal (it will only be necessary to determine one of the two transaminases).
- 8. Severe chronic liver disease as evidenced by, but not limited to, any of the following: International Normalized Ratio (INR) > 1.4, hypoalbuminemia, portal vein hypertension including presence of otherwise unexplained splenomegaly and history of esophageal varices.
- 9. Patients with known IgM seropositive tests for cytomegalovirus and/or Epstein-Barr virus in the previous month.
- 10. Patients with an active viral infection at screening for Hepatitis B Virus (HBV), Hepatitis C Virus (HCV) or detectable virus charge of HIV.
- 11. Intolerance to dexamethasone.
- 12. History of a bone marrow stem cell disorder.
- 13. Active or prior malignancy except adequately treated (i.e., complete surgical excision with negative margins) basal cell carcinoma in the last 5 years.
- 14. History of Helicobacter pylori by urea breath test or stool antigen test within 6 months of enrollment, if available.
- 15. History of myelodysplastic syndrome, systemic lupus erythematosus, or autoimmune cytopenia.
- 16. History of antiphospholipid antibody syndrome.
- 17. History of disseminated intravascular coagulation, hemolytic uremic syndrome, or thrombotic thrombocytopenic purpura.
- 18. History of deep or superficial venous thromboembolism in the last 12 months or stroke, acute ischaemic heart disease or acute peripheral vascular disease in the last 6 months.
- 19. Hypersensitivity to any recombinant Escherichia coli-derived product (e.g., Infergen, Neupogen, Somatropin, and Actimmune) or known sensitivity to any of the products to be administered during dosing

- 20. Currently enrolled in another investigational device or drug study or < 30 days since ending another investigational device or drug studies, or receiving other investigational agents.
- 21. Will have any other investigational procedures performed while enrolled in this clinical study.
- 22. Pregnant or breastfeeding, or planning to become pregnant or breastfeed during treatment or within 1 month after the end of treatment.
- 23. Female subject of childbearing potential is not willing to use, in combination with her partner, an acceptable method of effective contraception during treatment and for 1 month after the end of treatment (see annex 5 for additional contraception information). Females of childbearing potential should only be included after a negative pregnancy test.
- 24. Will not be available for protocol-required study visits, to the best of the subject's and investigator's knowledge.
- 25. Any kind of disorder that, in the opinion of the investigator, may compromise the ability of the subject to give written informed consent and/or to comply with all required study procedures.
- 26. Other serious comorbidities at investigator criteria.

c. Randomization procedures

Each subject who enters into the screening period for the study (when the subject signs the informed consent) will receive a unique subject identification number before any study-related activities/procedures are performed. The subject identification number will be assigned by the eCRF. This subject identification number will be used to identify the subject throughout the clinical study and must be used on all study documentation related to that subject.

Subjects who are determined not eligible after screening must be screen-failed in the eCRF and the reason for the screen failure provided.

Upon confirmation of eligibility, the site staff will use the eCRF to randomise a subject. Randomization of the patient is authorized until 72 hours after signing the informed consent. Randomization will be stratified by center with a 1:1 allocation using random block sizes to receive:

- Dexamethasone 40 mg daily x 4 days only in the first cycle and subcutaneous romiplostim weekly (ROM + DEX arm) for up to 12 months (365 days).
- Dexamethasone 40 mg daily x 4 days for up to 3 cycles every 14 to 28 days (DEX arm).

The investigator is responsible to document the decision to enroll the patient into the study and will note and date the information in the subject's medical record and in/on the enrolment CRF. Subjects will be considered enrolled upon randomization in the eCRF. The subject identification number must remain constant throughout the entire clinical study.

Romiplostim will be sent to the site upon subject screening.

d. Blinding procedures

Not applicable. Open label study.

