 - Definition of 6mSROT-30: platelets higher or equal than 30x10⁹/L in the absence of any ITP treatment including any rescue treatment

for at least 6 consecutive months (≥180 days) from treatment cessation and without WHO grade 2 or more bleeding.

- To evaluate the difference between study arms in the proportion of patients achieving 12mSROT-50 at 12 months (365 days) from treatment cessation.
 - Definition of 12mSROT-50: platelets higher or equal than 50x10⁹/L
 in the absence of any ITP treatment including any rescue treatment
 for at least 12 consecutive months (≥365 days) from treatment
 cessation and without WHO grade 2 or more bleeding.
- To evaluate the difference between study arms in the proportion of patients achieving 12mSROT-30 at 12 months (365 days) from treatment cessation.
 - Definition of 12mSROT-30: platelets higher or equal than 30x10⁹/L in the absence of any ITP treatment including any rescue treatment for at least 12 consecutive months (≥365 days) from treatment cessation and without WHO grade 2 or more bleeding.
- To evaluate the difference between study arms in the proportion of patients with complete response (CR) at 6 months (Day 180), at 12 months (Day 365) from randomisation and End of study Visit (visit 12 months after the last dose of study treatment). We will evaluate this in the total sample and in the absence of any rescue treatment
 - Definition of CR: platelet count ≥100x10⁹/L and absence of bleeding symptoms.
- To evaluate the difference between study arms in the proportion of patients with response (R) at 6 months (Day 180), at 12 months (Day 365) from randomisation and End of study Visit (visit 12 months after the last dose of study treatment). We will evaluate this in the total sample and in the absence of any rescue treatment
 - Definition of R: platelet count between 100x10⁹/L and 30x10⁹/L and at least doubled from baseline and absence of bleeding symptoms.
- To evaluate the difference between study arms in the proportion of patients with global response (GR) at 6 months (Day 180), at 12 months (Day 365) from randomisation and End of study Visit (visit 12 months after the last dose of study treatment). We will evaluate this in the total sample and in the absence of any rescue treatment
 - o Definition of GR: CR or R.

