- To evaluate the difference between study arms in the proportion of patients with response within the target range (TR) at 6 months (Day 180), at 12 months (Day 365) from randomisation and End of study Visit (visit 12

months after the last dose of study treatment). We will evaluate this in the total sample and in the absence of any rescue treatment

- Definition of TR: platelet count between ≥30x10⁹/L and ≤400x10⁹/L.
- To evaluate the difference between study arms in the median time to first response defined as the time from randomization to first response (R) in the absence of any rescue treatment. We will evaluate this in the total sample and in the absence of any rescue treatment.
- To evaluate the difference between study arms in the proportion of patients with early response (ER) and initial response (IR).
 - Definition of ER: proportion of patients with platelet count higher or equal than 30x10⁹/L and at least doble than baseline at first week (Day 7) from randomisation.
 - Definition of IR: proportion of patients with platelet count higher or equal than 30x10⁹/L in the first month (Day 30) from randomisation.
- To compare the difference of means between study arms of the maximum number of consecutive days with platelet response (CR, R, GR and TR) along the study period. We will evaluate them in the total sample and in the absence of any rescue treatment
- To compare the difference of means between study arms of the total number of days with platelet response (CR, R, GR and TR) along the study period. We will evaluate them in the total sample and in the absence of any rescue treatment.
- To evaluate and to compare the proportion of patients who need rescue treatments and proportion and time to treatment failures
- To compare the time to loss of response (LoR) in patients who achieved response in both arms.
 - Definition of LoR: number of days from the first time the patient achieved a platelet count ≥30x10⁹/L until platelet count dropped below 30x10⁹/L measured on 2 occasions with more than 1 day apart or presence of bleeding
- To compare the difference between study arms in the proportion of patients requiring any rescue treatment along the study period.

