All patients who are randomized will be included in the ITT Population. The ITT Population will be used to summarize subject disposition and baseline characteristics. Patients will be analysed according to the treatment they were allocated to at randomization; not necessarily the treatment they actually received. Results will be presented "as randomized."

mITT Population

All patients who are randomized and received at least one dose of study medication will be included in the mITT Population. The mITT Population is the primary analysis population for efficacy. Patients will be analysed according to the treatment they were allocated to at randomization; not necessarily the treatment they actually received. Results will be presented "as randomized."

rITT Population

All patients who are randomized and received at least one dose of study medication and achieved response (R) at any time during the study will be included in the rITT Population. The rITT Population will be used for the analysis of time to loss of response. Patients will be analysed according to the treatment they were allocated to at randomization; not necessarily the treatment they actually received. Results will be presented "as randomized."

d. Analysis of Primary Objective

The primary endpoint is 6mSROT-50 rate at 6 months (180 days) from treatment cessation.

The proportion of patients with 6mSROT-50 and corresponding 95% CIs for each study arm will be provided. A Chi-square test or Fisher test if applicable, will be used to compare the proportion of 6mSROT-50 between treatment arms.

e. Analysis of Secondary Objectives

i. Secondary Efficacy evaluations

For the analysis of the secondary endpoints, following analyses will be conducted:

- The proportion of patients with 6mSROT-30, 12mSROT-30 and 12mSROT-50 and corresponding 95% CIs for each study arm will be provided. A Chi-square test or Fisher test if applicable will be used to compare the proportion of each endpoint between treatment arms.
- The proportion of patients with CR, R, GR or TR at 6 and 12 and End of study Visit (visit 12 months after the last dose of study treatment) will be calculated and corresponding 95% CIs for each study arm will be provided. A Chi-square test or Fisher test if applicable will be used to compare the proportion of each endpoint between treatment arms.

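### IR and TR can be met by an unchanged, bleeding patient who enters at 30–49×10⁹/L, and the LoR clock can start, and record a loss, before the response that defines its analysis set

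*Protocol*

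**What the plan says.** All counts below are in units of 10⁹/L.

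- **Eligibility** (Protocol 1.l and 7.a, criterion 3): "Platelet counts <30x10⁹/L or ITP with platelet counts <50x10⁹/L and concomitant bleeding symptoms". A count of 30–49 is allowed if the patient is bleeding.
- **IR** (1.j, 6.c): "Definition of IR: proportion of patients with platelet count higher or equal than 30x10⁹/L in the first month (Day 30) from randomisation".
- **TR** (1.j, 6.c): "Definition of TR: platelet count between ≥30x10⁹/L and ≤400x10⁹/L". TR is assessed at Day 180, Day 365 and the End of study Visit. It is also one of the responses counted in the maximum consecutive days and total days with platelet response.
- **6mSROT-30** (1.j, 6.c): "Definition of 6mSROT-30: platelets higher or equal than 30x10⁹/L in the absence of any ITP treatment including any rescue treatment", continuing "for at least 6 consecutive months (≥180 days) from treatment cessation and without WHO grade 2 or more bleeding". 12mSROT-30 is the same over at least 365 days.
- **LoR** (1.j, 6.c): "Definition of LoR: number of days from the first time the patient achieved a platelet count ≥30x10⁹/L until platelet count dropped below 30x10⁹/L" on two occasions, or until bleeding is present. No bleeding grade is set.
- **LoR analysis set** (11.c): randomised and treated patients who "achieved response (R) at any time during the study will be included in the rITT Population".

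By contrast, ER at Day 7 needs a count of at least 30 and at least twice baseline. R needs 30–100, at least a doubling, and no bleeding symptoms. CR needs at least 100 and no bleeding symptoms. The primary endpoint, 6mSROT-50, uses a threshold of 50.

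**The concern.** The protocol recognises that a bare threshold is not a response when patients may enter above it: R and ER carry a doubling condition. IR, listed directly after ER, does not, and neither does TR. For entrants at 30–49, these two measures can be satisfied by the state that made the patient eligible.

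LoR has a different fault. Membership of the analysis set depends on R, but time zero depends on a weaker event, the first count of at least 30. Bleeding is itself a loss event, so the rule as written can date a loss before the response that is supposedly lost.

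At stake are the readability of IR, TR and the TR day counts as measures of treatment response, and the early part of the LoR curve. These rules are written into 1.j and 6.c, so an analysis that applies them faithfully reproduces the fault.

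**Working it through.** **1. Apply each definition to a patient whose count never changes**

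| Baseline = later count | IR (≥30) | TR (30–400) | SROT-30, platelet part | Count needed to double | ER, R | CR (≥100) | SROT-50, platelet part |
|---|---|---|---|---|---|---|---|
| 30 | met | met | met | 60 | not met | not met | not met |
| 35 | met | met | met | 70 | not met | not met | not met |
| 40 | met | met | met | 80 | not met | not met | not met |
| 49 | met | met | met | 98 | not met | not met | not met |

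IR and TR have no bleeding condition, so they are met even if bleeding continues. The same patient fails ER at Day 7 and passes IR at Day 30. For SROT-30, only the platelet part is met.

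**2. Follow the LoR clock**

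- Baseline 40, bleeding. R needs a count of 80–100 without bleeding. Read literally, the clock starts at Day 1 or at the first later visit with a count of at least 30. If the patient is bleeding then, a loss is recorded at about day 0. If R is reached later, the patient enters rITT carrying that loss.
- Baseline 20, rising to 35 with residual bleeding. The count is at least 30, so the clock starts. R is not met (doubling needs 40, and bleeding is present). The bleeding is again a loss at about day 0. The start-point fault is therefore not confined to the 30–49 entrants.

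**3. Size**

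The only design rates in the protocol are those for 6mSROT-50 (11.b): 30% against 56.6%, two-sided 5%, 80% power, 15% dropout, 63 per arm. To reproduce that figure, use the pooled-variance formula

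n = [1.960·√(2·0.433·0.567) + 0.842·√(0.30·0.70 + 0.566·0.434)]² / 0.266² = 53.3, so 54 per arm.

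54/0.85 = 63.5 (64 rounded up), and 54×1.15 = 62.1 (63 rounded up). The stated 63 is reproduced within rounding. Power with 63×0.85 = 53.55 evaluable per arm is 80.2%.

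The protocol gives neither the share f entering at 30–49 nor rates for IR, TR or SROT-30. As an illustration only, borrow the primary rates for the other patients and count every 30–49 entrant as a responder in both arms. Each rate becomes (1−f)·p + f, and the difference becomes (1−f)×26.6 points.

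| f (assumed) | Such patients per 63 | DEX | ROM+DEX | Difference (points) | Power at 53 per arm |
|---|---|---|---|---|---|
| 0 | 0 | 30.0% | 56.6% | 26.6 | 80% |
| 5% | 3.2 | 33.5% | 58.8% | 25.3 | 75% |
| 10% | 6.3 | 37.0% | 60.9% | 23.9 | 70% |
| 20% | 12.6 | 44.0% | 65.3% | 21.3 | 60% |
| 30% | 18.9 | 51.0% | 69.6% | 18.6 | 50% |

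Within this illustration the shrinkage is a maximum, because some of these entrants will fall below 30.

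**4. Would doubling suit every ≥30 endpoint?**

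Doubling exceeds 50 once baseline exceeds 25. With baseline 40 and a steady count of 60 off treatment without grade 2 bleeding, SROT-50 is met (60 ≥ 50), but a doubled SROT-30 would fail (60 < 80). The secondary would then be stricter than the primary, and the nesting of the 30 and 50 thresholds would be lost. For TR, a patient entering at 45 and now at 85 would fall outside the target range (85 < 90), which defeats a range measure.

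**The case against.** The strongest defence is that little depends on this. The primary threshold of 50 lies above every permitted entry count. ER, R, CR, GR and time to first response (R) are untouched. GR is reported at the same time points as TR, so a measure without this fault stands beside it. Section 11.e declares the secondary endpoints exploratory and unadjusted. Randomisation balances the 30–49 entrants on average, and stratifying by centre alone is no defect in itself. All of this stands, and it limits the weight of the point.

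Three stronger readings are tempting, and the protocol does not support them.

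- *A reader might infer that these patients meet SROT-30 on entry.* They cannot. It needs 180 or 365 consecutive days after treatment cessation, off all ITP and rescue treatment, without WHO grade 2 or more bleeding. In the ROM+DEX arm, section 9.b also has counts below 50 leading to dose increases and continued romiplostim up to Day 365, so such a patient does not simply drift into success.
- *A reader might infer that LoR counts unchanged disease as response.* It does not, because an unchanged patient never reaches R and never enters rITT. The fault is the start point.
- *A reader might take the fall from 26.6 to 18.6 points as the expected loss.* The 26.6 belongs to the primary endpoint and the shares are assumed.

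It can also be said that event derivation belongs in the statistical analysis plan. That would answer a silence, but here the protocol states the start point and the event explicitly.

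**Conclusion.** The point holds for IR and TR (with the TR-based day counts) and for the LoR start point. It follows from the wording alone and needs no assumption, except that the day-0 loss for a 30–49 entrant on Day 1 requires the entry count to qualify as a count achieved. The baseline-20 example does not need that reading.

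For SROT-30 the point is weaker: it lacks a rise-from-baseline condition, but its treatment-free and bleeding conditions do most of the work.

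The expected effect is inflated rates in both arms and some dilution of the difference, plus artificial early events in the LoR curve. Directional bias is not expected, and the primary analysis is not threatened. The size cannot be fixed from the protocol. The table above shows how dilution scales with an assumed share, on borrowed rates and at its upper bound. It is not an estimate for IR, TR or SROT-30.

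**What to change.** In 1.j and 6.c:

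1. **IR:** add the condition that the count is at least doubled from baseline, as ER has.
2. **LoR:** start the clock at the first visit meeting R or CR, and count only loss events after that visit. The rITT definition in 11.c names R alone, so check it against the same starting event.
3. **TR, 6mSROT-30 and 12mSROT-30:** leave the definitions unchanged, for the reasons in step 4 of the working. Add a sensitivity analysis of TR and SROT-30 that excludes patients with a baseline count of 30×10⁹/L or more.

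The cost is wording and one sensitivity analysis. Baseline counts, visit counts and bleeding assessments are already collected, and the sample size does not change. The downside is slightly lower IR rates. This includes some patients outside the 30–49 group: for any baseline above 15, doubling asks for more than 30, so a patient going from 20 to 35 would no longer be an IR, just as that patient would not be an ER now.

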8. WITHDRAWAL CRITERIA

a. Screening failure

Screening failures are patients who do not fulfill the eligibility criteria for the study, and therefore must not be enrolled and randomised. These patients should have the reason for study withdrawal recorded as "eligibility criteria not fulfilled". This reason for study withdrawal is not valid for randomized patients.

Patients can be rescreened a single time, but they cannot be re-randomized.

b. Reasons for Withdrawal

Patients may withdraw from treatment at any time.

The Investigator may discontinue study treatment for any of the following reasons:

- Patient desires the discontinuation of treatment (i.e., withdraws consent for treatment).
- No response to study treatment.
- Adverse event that, in the opinion of the investigator or the sponsor, contraindicates further dosing.
- Pregnancy or intention to become pregnant.
- Subject noncompliance that, in the opinion of the investigator or sponsor, warrants withdrawal; e.g., refusal to adhere to scheduled visits.
- Noncompliance with study procedures.
- Intercurrent illness or worsening of a chronic condition.

The primary reason for withdrawal from treatment will be documented in the eCRF.

If the reason for withdrawal is an AE, the patient will be followed by the Investigator until such events resolve, stabilize, and, according to the Investigator's judgment, there is no need for further follow-up.

A patient who withdraws consent will always be asked about the reason for withdrawal and the presence of any AE. The Investigator will follow up AEs outside of the clinical study.

If a patient withdraws from participation in the study, then his or her randomization or patient identification number cannot be reused. Withdrawn patients will not be replaced.

Reasons for removal of a subject from the study are:

- Decision by sponsor
- Withdrawal of consent from study
- Death
- Lost to follow-up
- No response treatment failure

c. Handling of Withdrawals

Subjects who are permanently discontinued from receiving study treatment will be followed for safety, including the collection of any protocol-specified information, unless consent is withdrawn or the subject is lost to follow-up. All subjects will be followed for 12 months since randomization, and minimum 6 months after stopping the study treatment (both arms).

The investigator will be requested to collect all patient data until he/she left the study.

d. Lost to follow-up

A subject will be considered lost to follow-up if he or she repeatedly fails to return for scheduled visits and is unable to be contacted by the study site.

The following actions must be taken if a subject fail to return to the clinic for a required study visit:

- The site must attempt to contact the subject and reschedule the missed visit as soon as possible and counsel the subject on the importance of maintaining the assigned visit schedule and ascertain whether or not the subject wishes to and/or is able to continue in the study.
- In cases in which the subject is deemed lost to follow-up, the investigator or designee must make every effort to regain contact with the subject

(where possible, 3 telephone calls). These contact attempts are to be documented in the subject's medical record.

• If the subject continues to be unreachable, he/she will be considered to have withdrawn from the study with a primary reason of lost to follow-up.

e. Reserve and Replacement Subjects

Randomised subjects will not be replaced.

f. Prematurely termination or suspension of the study

This study may be temporarily suspended or prematurely terminated by the sponsor if there is sufficient reasonable cause. Written notification, documenting the reason for study suspension or termination, will be provided by the sponsor to the IRB/IEC and Health Authorities.

Circumstances that may warrant termination or suspension include, but are not limited to:

- Determination of unexpected, significant, or unacceptable risk to participants
- Demonstration of efficacy that would warrant stopping.
- Insufficient compliance to protocol requirements.
- Data that are not sufficiently complete and/or evaluable.
- Determination of futility.

